## 1. BACKGROUND

Heart failure (HF) is a non-communicable disease (NCD) that affects more than 38 million people globally.(1,2) In sub-Saharan Africa (SSA), HF is responsible for up to 7% of hospital admissions and a high premature mortality rate.(3,4) HF is a clinical syndrome with diverse causes, such as hypertension and rheumatic heart disease, that results in multiple debilitating symptoms. These symptoms can often be managed by patients themselves, when given the tools to engage in self-care. Self-care is a World Health Organization-endorsed intervention for NCD with a strong evidence base and critical advantages in low-resource settings. It benefits both patients and health systems by shifting fundamental care tasks from providers to patients while empowering patients and enhancing well-being.(5) Self-care for HF includes behaviors such as controlling dietary intake of sodium and recognizing and treating symptoms such as shortness of breath. Despite its benefits, self-care for HF remains underutilized globally, especially in low- and middle-income countries (LMIC).(6) In Uganda, self-care is identified as one of the greatest unmet needs among patients with HF.(7) mHealth offers a promising platform to close this performance gap in LMIC, by leveraging the widespread penetration of mobile phones to offer individualized self-care tools such as education, healthy lifestyle messaging, and decision support directly to patients with HF.(8-10)

In 2016, our multi-national team began collaborating to adapt Medly, a smartphone-based mHealth application for self-care of HF, developed and tested in Canada, to the setting of Uganda. Medly was shown to improve self-care and health-related quality of life (HRQoL) in HF by generating personalized self-care instructions based on patient-entered symptoms and vital signs transmitted by telemonitoring devices. Through formative work among patients with HF and providers at the Uganda Heart Institute (UHI) in Kampala, we learned that patients commonly have significant HF symptoms but do not routinely engage in self-care. This is due to lack of knowledge about self-care options and actions to take in response to symptoms. Despite this, both providers and patients were optimistic about a mHealth application that could improve self-care in HF.

Our research team has designed Medly Uganda for low-cost feature phones using a simpler interface with an algorithm that generates self-care instructions based on patient-reported symptoms alone. We have based the app on the Unstructured Supplementary Service Data (USSD) platform, a universally available interface that enables users to navigate hierarchical menus and offers multiple advantages for mHealth, including enhanced security features, verifiable transactions, simple navigation, and real-time interaction. (11,12) Though the Short Messaging Service (SMS) platform has been more widely used in mHealth, Ugandans commonly use and trust USSD for secure Mobile Money transactions. Furthermore, we designed a simple, secure, webbased dashboard for clinicians to monitor safety alerts generated by the app based on patient symptom reporting. Finally, we embedded Medly Uganda within FamilyConnect (FC), a Ugandan government-endorsed, hybrid USSD-SMS platform with proven feasibility and user engagement that currently provides pregnant women with health education and self-care recommendations. No member of the research team stands to profit financially from the current project or future iterations of Medly Uganda.

## 2. AIMS

Self-care is an important, yet underutilized, intervention in the management of chronic conditions, especially for low-resource settings because it shifts fundamental care tasks from providers to patients while empowering patients and enhancing quality of life. In this project, we will study the implementation and preliminary clinical effectiveness of Medly Uganda, a patient-facing mobile health application designed to improve self-care among patients within heart failure. The multi-level engagement of stakeholders and the grounding in user-centered design principles will serve to enhance the feasibility and scalability of Medly Uganda.

**AIM 1:** Assess the implementation of Medly Uganda at the Uganda Heart Institute in Kampala, Uganda. We will use mixed methods to assess feasibility, acceptability, and adoption of the app and accompanying provider dashboard. Sources of data will include surveys and interviews with patient and clinician participants and app and dashboard usage data.

**AIM 2:** Assess the preliminary effectiveness of Medly Uganda on clinical outcomes. Our primary outcome is improvement in the Self-Care in Heart Failure Index, a widely used, evidencebased instrument which we will evaluate at 0,3, and 6 months. We will also assess changes in HRQoL using the brief EQ-5D tool as well as the 6-Minute Walk Test, left ventricular ejection fraction, and frequency of acute care visits at the same time points.

## 3. STUDY PROTOCOL

### 3.1. Study Setting

Uganda is a low-income country in East Africa with a population of 35 million and a rising burden of NCD. Resource allocation toward NCD has been poor and the capacity of public sector healthcare facilities to

address NCD, including HF, is low. The proposed project will be conducted at UHI, the highest level referral center for cardiac care in the country and the only public sector facility with robust HF services. UHI is located on the campus of Mulago National Referral Hospital in the capital city, Kampala. Its outpatient clinic serves 70-100 adult patients per day from throughout Uganda and neighboring countries and from across socioeconomic and demographic spectra. Clinical care is provided by 12 physicians, 6 fellows, and 18 nurses. The coordinating center for this project is the Uganda Initiative for Integrated Management of Non-Communicable Disease (UINCD), a research consortium co-directed by the co-Principal Investigators (PI) UINCD headquarters are located on Mulago campus, thereby allowing for ease of communication and collaboration between the clinical research site and the coordinating center.

In Uganda, in 2016, there were 22 million active mobile phone accounts and 340,000 land-lines, a ratio similar to other LMIC where mobile telephony became ubiquitous while circumventing land-line infrastructure. Cellular signals of the three main carriers are strong throughout the country. Given these features, Uganda has seen numerous mHealth pilot studies, many of which failed to progress beyond pilot stage due to lack of contextually appropriate design and testing and lack of engagement with key stakeholders. In response to this so-called “pilotitis”, all mHealth projects are now required to exhibit genuine local ownership/co-ownership and collaboration with relevant government entities, which we demonstrate in the current proposal.

### 3.2. Study Design

This is a single-center prospective cohort study conducted at UHI. The study period is 6 months. Patient participants will have three study timepoints (Baseline, Month 3, and Month 6) while data will be collected from clinician participants only at Month 6.

### 3.4. Procedures

Study procedures will be conducted by the Research Nurse (RN), unless otherwise noted. A Research Assistant (RA) with experience in qualitative data collection will conduct semi-structured interviews (SSI) and assist the RN with data collection. Quantitative data will be entered directly into a secure, UINCD tablet using Qualtrics software. Qualitative data will be audio recorded using a UINCD recording device. We will have samples of the two most common feature phones and

[figure not shown]

Figure 1. Flow diagram illustrating study design of current proposal, key milestones leading to current proposal, and anticipated next steps

smartphones onsite to allow participants who do not have a phone with them at this time to fully participate in on-site study procedures (registration and on-boarding). There are three study timepoints for patient participants: Baseline, Month 3, and Month 6. Study procedures include multiple widely used, validated clinical measurements: Self-Care in Heart Failure Index (SCHFI), EQ-5D, Six-Minute Walk Test (6MWT), and limited transthoracic echocardiogram for measurement of Left Ventricular Ejection Fraction (LVEF). Echocardiograms will be performed by a UHI cardiologist but interpreted en bloc and blinded at study conclusion to avoid interpretation bias. At Baseline, participants will complete informed consent, register in FC, orient to the app and message content, and conduct mock sessions until comfortable using the system, as determined by RN. We will also collect weight, vital signs, and a list of prescribed medicines. Urine pregnancy test will be done on women of childbearing age. SCHFI, EQ-5D, 6MWT, and LVEF will be completed. Clinician participants will be oriented to the app, dashboard, and expectations regarding their use by the RN. At Month 3, RN will review app activity with the participant and re-educate or re-orient them to the app, as needed. SCHFI, EQ-5D, 6MWT, and LVEF will be repeated. At Month 6, SCHFI, EQ-5D, 6MWT, and LVEF will be repeated. Participants will complete a feasibility survey and the RA will conduct an SSI using an interview guide (Appendix). Since the app is used on their personal phone, they will retain this device. Following the Month 6 visit, patient participants will be able to continue using Medly Uganda, however, depending upon the funding environment, may be responsible for associated USSD and SMS costs. Upon completion of Month 6 procedures by all active patient participants, clinician participants will complete a modified feasibility survey and the RA will conduct an SSI using a different interview guide.

Procedure	Comments
SCHFI	22-item instrument validated and used in LMIC settings. (6, 34)
EQ-5D	Generic, five-item HRQoL instrument validated and used in LMIC settings and for HF.(15, 60-64)
6MWT	Reproducible, submaximal exercise test to assess functional capacity in patients with cardiopulmonary conditions, including HF. Strong, independent predictor of morbidity and mortality in patients with HF. Measured in total distance walked independently in six minutes.(65-67)
LVEF	Widely recognized prognostic marker in HF and clinical outcome in HF self-care research. Percentage of blood ejected during systole.(68)

Table 1. Procedures include Self-Care in Heart Failure Index (SCHFI), EQ-5D, Six-Minute Walk Test (6MWT), and Left Ventricular Ejection Fraction (LVEF).

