### 3.4. Inclusion/Exclusion Criteria:

We will use consecutive sampling to identify potential patient participants. Based on UHI patient volume and demographics, we anticipate an equal distribution of urban- and rural-dwellers and 60:40 female:male ratio. For the clinician sample, we will seek to enroll all clinicians who meet inclusion/exclusion criteria (n=5 nurses; 5 doctors).

Patient inclusion criteria include: 1. UHI patient presenting for routine or urgent outpatient visit; 2. Currently living in Uganda and not planning to travel abroad for six months; 3. Age  $\geq 18$  years; 4. Symptomatic (New York Heart Association Class II, III, or IV) HF regardless of LVEF; 5. Access to a mobile phone; 6. Basic reading skills in English, Luganda, and/or Runyankole.

Patient exclusion criteria include: 1. Life expectancy  $<$  six months; 2. Active medical condition requiring hospitalization, such as cardiac ischemia (acute electrocardiographic changes and/or positive biomarkers, if available), syncope, or significant fluid overload; 3. Pregnancy; 4. Inability to provide informed consent.

Clinician inclusion criteria include: 1. UHI staff doctor or nurse; 2. Anticipated assignment to Medly Uganda duties at least once during the study period.

Clinician exclusion criteria includes unwillingness to provide informed consent.

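### Collector, mode and order of the self-care questionnaire are not fixed; by default the nurse who trains patients on the app collects it, so a reporting shift between Baseline and follow-up would count as improvement

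*Combined protocol and SAP*

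**What the plan says.** **Who collects.** Section 3.4 Procedures opens with a default: "Study procedures will be conducted by the Research Nurse (RN), unless otherwise noted". It then lists SCHFI and EQ-5D among the study procedures and assigns neither to anyone else. The Research Assistant "will conduct semi-structured interviews (SSI) and assist the RN with data collection", which gives no specific role in the questionnaires. Data go straight into a study tablet. Whether the patient or a staff member completes the items is not stated.

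**Who trains.** At Baseline patients "conduct mock sessions until comfortable using the system, as determined by RN". At the next visit: "At Month 3, RN will review app activity with the participant and re-educate or re-orient them to the app, as needed".

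**Order as listed.** Baseline: consent, registration, app orientation, mock sessions, weight and other measurements, then SCHFI and EQ-5D. Month 3: app-activity review and re-education, then SCHFI and EQ-5D. Month 6: SCHFI and EQ-5D, then the feasibility survey and the interview, with no app review or re-education listed.

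**Protection against assessment bias.** Echocardiograms are "interpreted en bloc and blinded at study conclusion to avoid interpretation bias". Nothing comparable is written for the questionnaires.

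**Outcome and analysis.** Section 4.3 (Aim 2) makes change in the SCHFI Management scale the primary outcome, a Likert questionnaire on patients' own actions, scored to 100. Section 3.2 describes a single-center cohort. The paired t-test, or the Wilcoxon signed rank test, for change at Months 3 and 6 stands in 4.2.

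**The concern.** The Management scale asks whether patients notice symptoms and act on them, which is what the app's messages teach (3.4 Intervention). If the person asking is also the person who taught the app and has just gone through the patient's usage, the patient has a reason to give the taught answer whether or not behaviour changed. The plan recognises this kind of problem for LVEF, a secondary outcome that does not depend on patient report, but not for the primary outcome. Section 4.3 on potential challenges does not mention response or assessor bias.

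At stake is the reading of Aim 2. No comparison group is described, so a rise in reporting cannot be told apart from a rise in self-care, and the study's own data cannot estimate it afterwards.

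**Working it through.** **1. What can bias the result.** Let δ be the true mean change, b₀ the mean reporting bias at Baseline and b_t the mean reporting bias at follow-up. The expected observed change is

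δ + (b_t − b₀).

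If b_t = b₀, the bias cancels. Only the net shift b = b_t − b₀ matters.

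**2. What the listed order implies for each visit.**

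| Visit | Listed before SCHFI | Consequence |
|---|---|---|
| Baseline | App orientation and mock sessions, judged by the nurse | b₀ may already be raised |
| Month 3 | App-activity review and re-education by the nurse | b₃ may be raised by fresh coaching |
| Month 6 | No coaching listed | Only the nurse's standing as trainer remains |

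The plan does not make b equal to zero at either follow-up, and does not fix its sign. A positive b would be counted as improvement; a negative b would hide some.

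**3. The plan's own figure.** Section 4.1 gives 54 evaluable patients for a 10-point change, SD 25, two-sided 0.05, power 0.90. The normal approximation is

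n = [25 × (1.960 + 1.282) / 10]² = 65.7, so 66 (68 with the t distribution).

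Power at n = 54 is 0.82 by noncentral t. The figure 54 matches a one-sided 0.05 calculation: [25 × (1.645 + 1.282) / 10]² = 53.5. The step to 72 is right: 54 / 0.75 = 72. This mismatch is a separate matter and neither supports nor weakens the present point. I use n = 54 and SD 25 below because they are the plan's inputs.

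**4. Illustration of a net shift with δ = 0.** The standard error is 25/√54 = 3.40 and the two-sided critical t on 53 degrees of freedom is 2.006. The smallest significant mean change is 2.006 × 3.40 = 6.8 points. For an assumed shift b, the noncentrality is b/3.40, and the probability of p < 0.05 follows from the noncentral t distribution:

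| Assumed b (points) | Noncentrality | n = 54 | n = 72 |
|---|---|---|---|
| 0 | 0 | 5% | 5% |
| 2 | 0.59 | 9% | 10% |
| 3 | 0.88 | 14% | 17% |
| 4 | 1.18 | 21% | 27% |
| 5 | 1.47 | 30% | 39% |

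The last column applies if all 72 enrolled patients complete. For b of 3 points or more nearly all of each probability is false improvement; under b = 0 that direction accounts for 2.5%.

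The documents give no value for b, so the rows are a range and not an estimate. They would apply to a shift of this size from any cause in an uncontrolled paired analysis. They do not isolate the part due to who asks the questions.

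**The case against.** **Month 6 is the powered timepoint, and no coaching is listed there.** This stands. A reader might infer that the primary result is collected straight after re-education; the documents support that sequence only for Month 3, and only as list order. Month 3 changes are tested as well (4.2), and at Month 6 the trainer is still the default collector.

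**Baseline SCHFI is also listed after contact with the trainer.** This stands too. A reader might infer that a single-arm design lets all desirability bias through. It does not: the constant part cancels, and a raised Baseline score could even shrink the observed change. But the two visits are not alike. One follows a first orientation; the others follow months of messages and a known trainer, so equal bias cannot be assumed.

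**Nurse collection is inferred.** Correct. No sentence says that the nurse puts the SCHFI questions, and collection by the assistant or by self-completion would fit the text. The reading that every patient is questioned by their own trainer minutes after coaching goes further than the documents. What they show is that this is the default and that nothing prevents it.

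**The percentages do not measure this defect.** Agreed; they are illustrative. Changing the collector would not cure the lack of a control arm, and patients would still know that they use the app.

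**Aim 2 is called preliminary, and less report-dependent outcomes exist.** LVEF, walking distance and record-abstracted visits give some support, but they do not correct the primary outcome.

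The text between 3.2 and 3.4 was not available for review, so a safeguard stated only there cannot be excluded.

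**Conclusion.** The point holds as a cheap improvement to the conduct of the primary assessment. It does not show that the result will be biased. The plan leaves collector, mode and order of SCHFI and EQ-5D open, and its default and listed order permit an avoidable difference in reporting between Baseline and follow-up. The exposure is clearest at Month 3 and weaker at Month 6.

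The size is unknown. If the net shift were 3 to 5 points, a study with no true change would be significant 14% to 30% of the time at n = 54. This assumes SD 25 as in 4.1, the paired t-test of 4.2 applied to the primary outcome (4.3 for Aim 2 names no test), and a shift that adds to every score on average. A 5-point shift is half of the 10-point target and, by itself, below the 6.8 points needed for significance.

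**What to change.** In 3.4 Procedures, state that SCHFI and EQ-5D are completed first at each visit:

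- Baseline: after consent, before app registration and orientation.
- Month 3: before the app-activity review and re-education.
- Month 6: before the feasibility survey and the interview. This is already the listed order; the sentence makes it binding.

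State also that the existing Research Assistant administers both instruments in the same mode at all three visits, without looking at that patient's app usage beforehand. Allow self-completion on the tablet only where the patient can manage it in the same way at every visit. The inclusion criterion, "Basic reading skills in English, Luganda, and/or Runyankole", does not by itself show that a patient can complete a 22-item instrument unaided.

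Adopt these parts together. Moving only the Baseline questionnaire ahead of orientation could lower b₀ and leave b_t unchanged, which would widen an upward net shift.

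**Cost.** A few protocol sentences, a change in visit order, brief questionnaire training for the assistant, whose stated experience is in qualitative work, and some workload moved from the nurse. No new staff or procedure is needed. Keeping the assistant unaware of usage takes some care, because the assistant also supports the nurse. Residual response bias remains and should be acknowledged as a limitation when the Aim 2 results are reported.

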### 3.4. Intervention

Participants will be asked to initiate a USSD session by dialing the Medly Uganda sub-code and entering a unique PIN every Monday, Wednesday, and Friday morning for six months and whenever they experience concerning symptoms. If a participant has not done so by 11AM on the designated days, RapidPro will generate an SMS reminder. Each interactive USSD session will present a series of symptom-based questions to the participant and be followed by a tailored SMS message. While USSD session content will not remain on the participant's phone, SMS' will. This allows participants to retain and review messages, thereby reinforcing educational content. There are four Status categories: Stable, Fluid Overload, Urgent, and Critical. If Stable, participants will be sent one of six encouraging and educational messages. If Fluid Overload, Urgent or Critical, patient participants will be sent a message that identifies the symptom and recommends an action and the on-duty nurse will be sent an accompanying alert. Urgent and Critical alerts will also be sent to the on-duty doctor (Algorithm- attached to HIC application). The nurse is expected to call the patient for Urgent and Critical alerts within 60 and 15 minutes, respectively. Nurse phone call interactions will be guided by a standard operating manual. One UHI nurse and one

UHI doctor will be designated rotating 'on-duty' responsibility to monitor clinician alerts and the dashboard seven days a week. The doctor will be available to provide clinical supervision to the nurse as needed and they will have a daily in-person or by-phone huddle around 4PM to review the prior 24 hours system activity. Drs.[name] or [name] will be available at all times to provide an additional layer of technical and clinical backup to the designated clinicians as needed.

[figure not shown]

Figure 3. Technical design of Medly Uganda including the integration of the patient-facing application and the clinician dashboard.

Clinicians will access the dashboard by smartphone or computer using a unique username and password and entering the patient participant's phone number. The dashboard then presents a screen that includes basic demographic information, baseline clinical information from study entry. The screen also includes a color-coded matrix that graphically displays how the patient answered each question and the assigned Status from the current

and every prior USSD session. These are populated with data from RapidPro via API. An accompanying screen then allows the clinician to briefly summarize the content of their phone call and visualize all prior call entries.

Both app and dashboard contain security features approved by appropriate local stakeholders. As with mobile money, app access requires a valid SIM card associated with the registered user as well as a PIN. Dashboard access requires a username and password stored in non-human-readable form as generated by the bcrypt JavaScript library in the dashboard's PostgreSQL database.

